12.2.11. Health Outcome/Quality of Life Analyses

The following will be carried out for each part separately.

Questionnaire compliance rates will be ascertained at each measurement time point until the end of study therapy including at discontinuation (Visit 801).

Summary descriptive statistics will be provided for the PRO data (FACT-Hep) at each assessment. This summary will include mean, standard deviation, median, minimum, maximum, and change from baseline. Scores will be evaluated both in aggregate (that is, median values for each study arm at a given time point) and individually, in which each patient's score on study is evaluated relative to his/her baseline score. Time to worsening of symptoms will also be evaluated, and longitudinal analyses, such as repeated measures, will be performed. FACT subscales, total score, trial-outcome index, and symptoms (FHSI-8) will be assessed per the established scoring algorithm.

Other exploratory longitudinal analyses may be performed.

12.2.12. Safety Analyses

Adverse event (AE) terms and severity grades will be assigned by the investigator using CTCAE v4.0. AE terms will also be derived from verbatims using the Medical Dictionary of Regulatory Activities.

All patients who received LY2157299 will be evaluated for safety. Safety analyses will include, but are not limited to, the following:

- all reported AEs, including seriousness, severity, and possible relationship to study drug, using CTCAE terminology and grades
- TEAEs, including seriousness, severity, and possible relationship to study drug, using CTCAE terminology and grades
- dose adjustments for any study therapy

- physical exam and other safety observations, including those specifically targeting monitoring for cardiac safety
- laboratory measures

Safety analysis may also estimate the difference in the incidence of AEs between the 2 doses and study parts, adjusting as necessary for baseline AFP levels or other important covariates.

12.2.13. Exploratory Analyses

Exploratory analyses/data mining will be carried out on imaging data, Fibrotest data, gene-expression data, rules-based medicine multi-analyte panel (MAP) data and tumor-tissue data as appropriate, investigating links between these data and clinical and PD efficacy endpoints. Other TGF- β -signaling pathway biomarkers will also be included in this analysis.

After Amendment (a), both Child-Pugh Class A patients and Child-Pugh Class B7 patients are eligible and are being treated as 1 group given the similarity between these groups of patients, but additional analyses will look at the contribution of both classes to the clinical endpoints. In addition, as of Amendment (a), patients with liver transplant on maintenance immunosuppressive therapy are eligible, and possible differences in safety and efficacy endpoints between patients with and without liver transplant will be investigated.

After Amendment (c), first-line Child Pugh A patients are included in the study. Similar analyses to those conducted for patients in Parts A and B will be carried out for patients in Part C.

Given the more limited number of patients to be enrolled in Part D and E, exploratory analyses will be carried out as appropriate.

12.2.14. Interim Analyses

There were 2 planned interim analyses in Amendment (a). The first interim analysis reviewed both safety and PK of LY2157299. Safety was assessed after 20 patients (10 patients/dose) had enrolled and completed 1 cycle of treatment. The PK interim analysis occurred after the PK sample on Day 15 had been collected from 20 patients (this was carried out after the safety review).

For enrollment to continue in either dose level, there had to be no evidence of cardiotoxicity in any patient at that dose level and no drug-related CTCAE Grade 3/4 toxicity that was not manageable. The PK of LY2157299 in HCC patients were compared to those of patients with glioblastoma observed in Study JBAH. Since only sparse sampling was performed in Study JBAK (Parts A and B), comparisons between the 2 populations were carried out by simulations (median and 20th and 80th percentiles) using the population PK model from Study JBAH.

The decision to continue was based on the following:

1. If neither dose was considered tolerable, then the study would be terminated.
2. If only 1 dose was considered tolerable, then enrollment would continue into this dose cohort, and the other dose cohort would close.

3. If the predicted 80th percentile of the distribution of AUC exceeded 10.96 (mg.h/L) for either dose, enrollment into this dose cohort may have been ceased.

Enrollment after the first interim analysis continued in both dose cohorts, and a second interim analysis was planned when an additional 30 patients had been enrolled in each arm (i.e., total of 40 patients in each arm) and had been actively followed for 3 months or progressive disease or death had been observed. This was to be after the second planned radiological assessment (planned every 6 weeks) and after the collection of biomarker (specifically AFP) samples for all patients. Any patient who was lost to follow-up or started a new anticancer therapy before 3 months had elapsed without an event being observed was not eligible for inclusion in the interim analysis.

The decision for dropping 1 of the 2 dose cohorts was to be based on a composite endpoint, including the number of patients who were free from progression at 3 months, amount reduction in AFP and other TGF- β related biomarkers from baseline (adjusting for baseline levels if needed), and safety.

For example:

1. If the observed mean percentage reduction from baseline in AFP concentrations in either cohort was more than 50%, enrollment into the dose cohort may continue.
2. If the difference in mean percentage change from baseline in AFP concentrations between the 2 doses is $>20\%$, then the dose with the lowest reduction from baseline may be dropped after taking into consideration the observed results for E-cadherin and other TGF- β related biomarkers.
3. Either dose or both doses will be dropped if there is evidence of cardiotoxicity and/or drug-related CTCAE Grade 3/4 toxicity that is not manageable in any patient.
4. If the number of patients who are free from progression at 3 months in either dose is 21 or less, then the dose level may be discontinued.
 - o This cut-off represents a risk of continuing when the true median TTP is not considered clinically meaningful over no intervention (that is, median TTP = 3 months) is 32% and of deciding not to continue when the true median TTP is considered meaningful (that is, median TTP = 4.5 months) is 11%. (Information for risks of an incorrect decision using other cutoff values will be provided in the SAP.)

Two effects of LY2157299 are of interest for changes in AFP levels – whether there is evidence of a reasonably sustained 50% or greater reduction from baseline (as this is considered indicative of clinical benefit) in either dose and whether there is a difference of 20% in the percentage change from baseline between the 2 doses (for example, 50% reduction at 300 mg/day and 30% reduction at 160 mg/day). With 40 patients enrolled at each dose cohort and an assumed within-patient coefficient of variation of 44% (data on file), there is at least 95% probability that treatment effect of 50% within a dose group will be detected as significant at the 5% significance

level. The more sensitive situation concerns the probability of detecting a difference of 20% in the percentage reduction in pre and postdose concentrations between the 2 dose groups in order to choose a dose at this stage. The power to detect a 20% difference in percentage reduction between the 2 doses is approximately 80%, at the 20% 2-sided significance level.

Analysis of the mean fold change from baseline of biomarker concentrations levels were to be estimated from a mixed-effects model with sampling time, dose and their interaction as fixed effects, baseline levels (either as a continuous variable or categorical [AFP: ≤ 400 ng/mL or > 400 ng/mL]) as a covariate and patient as a random effect. The choice of variance-covariance structure was to have depended on the data. Biomarker concentrations were to be log transformed prior to analysis. Specific details of these analyses will be provided in the SAP.

If at the second interim analysis, when a total of 40 patients had been enrolled at each dose and followed as described, results of the comparison between the doses were still inconclusive, the decision to either continue enrollment into both doses or to choose 1 dose was to be made after discussions between the investigator, Lilly, and study statistician.

However, the planned second interim analysis described in Amendment (a) was not carried out, but an additional data review was conducted. Based on this review, the decision was to close Cohort 1 and continue enrollment until 70 patients enrolled into Cohort 2. At the time of the decision, 64 patients had been treated.

As part of Amendment (b), the second interim analysis for Part A was changed and planned to be after the 70th patient enrolled into Cohort 2 and started Cycle 1. The purpose of this analysis was to help inform the decision to prepare for further development of the compound in patients with HCC with elevated AFP levels. This analysis was completed in December 2012 (Faivre et al. 2013).

The purpose of the interim analyses in Part B (interim analysis 3) and Part C (interim analysis 4) was to prepare for further development of the compound and to inform the decision as to whether all second-line HCC patients, irrespective of baseline AFP levels (Part B), and Child-Pugh B7 or B8 status (Part C) patients may benefit from treatment with LY2157299.

The timing of the interim analyses for Parts B and C was based on assuming Parts B and C are designed as a Simon's 2-stage design with the same characteristics as used in the original protocol: where the assumption of a poor treatment is if the proportion free from disease progression is 50% at 3 months (assumes median TTP = 3 months) and a good treatment is if the proportion free from disease progression at 3 months is 63% (assumes median TTP = 4.5 months). The operating characteristics of this design are as follows: The null hypothesis is that the true response rate is 50%. In the first stage, 18 patients will be accrued and actively followed for at least 3 months or until they have discontinued. If there are 8 or fewer patients free from disease progression in these 18 patients, this may be indicative that patients with normal AFP levels are not benefiting from the treatment. The additional 22 patients will be accrued for a total of 40. The null hypothesis will be 'rejected' at the end of Parts B and C if 22 or more patients out of 40 patients in each part are observed to be free from disease

progression at 3 months. This design yields a type I error rate of 15% and power of 78% when the true response rate is 63%.

From Amendment (c), the above calculations now only applied to the third interim analysis (for Part B, completed June 2013). Given the change in strategy for Part C to enroll and treat first line Child Pugh A or B7 patients in amendment (c), only safety reviews are planned while the study is ongoing. An additional analysis may be carried out if needed to help with clinical planning of the compound for treating first-line patients.

Safety reviews for Part D are planned to determine the LY2157299 dose in combination with ramucirumab. This will be after 3 patients have completed 1 cycle of treatment in Cohort 1 (LY2157299 80 mg BID) prior to escalating to Cohort 2 (LY2157299 150 mg BID). A further safety review will be carried out after 3 patients have completed 1 cycle in Cohort 2.

In Part E, safety data will be reviewed after 3 patients have completed one cycle. If the schedule is deemed to be tolerable (<33% DLTs in Cycle 1 and consideration of the overall safety profile in later cycles), an additional 20 patients will be enrolled in order to better characterize the safety of the schedule and allow comparison to safety, pharmacokinetics and efficacy seen in other cohorts. No additional interim analyses are planned for Part E.

The timing of the final analyses for each study parts' clinical study reports and the final database lock is provided in Section [7.1](#).

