With Amendment (c), the study planned to enroll approximately 190 patients: 109 patients have been enrolled in Part A (37 in Cohort 1, 72 in Cohort 2); 40 are planned for Part B, and 40 for Part C (amended to enroll Child Pugh A patients who had not received any prior systemic therapy and were to be treated with LY2157299 plus sorafenib in a safety lead-in followed by an expansion at the selected dose).

With Amendment (d) and the addition of Part D, an additional 15 patients may be enrolled. With Amendment (e) and the addition of Part E, approximately 23 additional patients may be enrolled.

The primary objective of the study now is to characterize the TTP distributions, the effect on TGF- β -associated serum biomarkers (for example, TGF- β , AFP, E-cadherin) and the relationship between biomarker response and efficacy endpoints of:

- 1) Each of the 2 doses of LY2157299 in second-line patients or patients ineligible to receive sorafenib with HCC who have elevated AFP levels (Part A, Cohorts 1 and 2),
- 2) In second-line patients or patients ineligible to receive sorafenib with HCC who have AFP levels $<1.5x$ ULN dosed at 300 mg/day (Part B),
- 3) In first-line patients with HCC treated with 2 doses of LY2157299 in combination with sorafenib. If the decision in Part C is to use only 1 treatment group in the expansion cohort, the results from patients at the other dose will simply be listed.
- 4) In second-line patients with HCC treated with LY2157299 given for 21 days on followed by 7 days off (Part E).

For efficacy endpoints, no formal hypothesis testing based on a priori power calculations is planned; rather differences in various endpoints (eg, hazard ratios for TTP, OS) between appropriate treatment groups will be estimated. Since Part C patients are different in 2 ways from patients in Parts A and B (first-line versus second-line and treated with LY2157299 in combination with sorafenib compared to LY2157299 monotherapy, respectively), the only estimate of differences between Parts A and/or B with Part C will be between Part C and the sorafenib-naive patients from Parts A and B. The interpretation of any estimate will be considered in light of the size of this subgroup.

Data from patients from Part D and E will be summarized separately from the data in Parts A, B, and C.

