1. If the observed mean percentage reduction from baseline in AFP concentrations in either cohort was more than 50%, enrollment into the dose cohort may continue.
2. If the difference in mean percentage change from baseline in AFP concentrations between the 2 doses is $>20\%$, then the dose with the lowest reduction from baseline may be dropped after taking into consideration the observed results for E-cadherin and other TGF- β related biomarkers.

3. Either dose or both doses will be dropped if there is evidence of cardiotoxicity and/or drug-related CTCAE Grade 3/4 toxicity that is not manageable in any patient.
4. If the number of patients who are free from progression at 3 months in either dose is 21 or less, then the dose level may be discontinued.
 - This cut-off represents a risk of continuing when the true median TTP is not considered clinically meaningful over no intervention (that is, median TTP = 3 months) is 32% and of deciding not to continue when the true median TTP is considered meaningful (that is, median TTP = 4.5 months) is 11%. (Information for risks of an incorrect decision using other cutoff values will be provided in the SAP. However, this planned interim was not carried out and this information was not provided.)

Two effects of LY2157299 are of interest for changes in AFP levels – whether there is evidence of a reasonably sustained 50% or greater reduction from baseline (as this is considered indicative of clinical benefit) in either dose and whether there is a difference of 20% in the percent change from baseline between the 2 doses (for example, 50% reduction at 300 mg/day and 30% reduction at 160 mg/day). With 40 patients enrolled at each dose cohort and an assumed within-patient coefficient of variation of 44% (data on file), there is at least 95% probability that treatment effect of 50% within a dose group will be detected as significant at the 5% significance level. The more sensitive situation concerns the probability of detecting a difference of 20% in the percentage reduction in pre and postdose concentrations between the 2 dose groups in order to choose a dose at this stage. The power to detect a 20% difference in percent reduction between the 2 doses is approximately 80%, at the 20% 2-sided significance level.

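### The 15% type I error and 78% power stated for the Part B two-stage rule do not belong to it; exact values are 31.8% and 88.6% as worded

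*Protocol*

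**What the plan says.** Protocol 12.2.14 and SAP 5.3.2 describe the same rule for progression-free status at 3 months. A poor treatment has a true proportion of 50% (median TTP 3 months) and a good one 63% (median 4.5 months). Eighteen patients enter the first stage. If 8 or fewer are progression-free, "this may be indicative that patients with normal AFP levels are not benefiting from the treatment". The text then continues: "The additional 22 patients will be accrued for a total of 40". The null is rejected at 22 or more of 40. Both documents conclude: "This design yields a type I error rate of 15% and power of 78"%, the power being at a true rate of 63%.

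Earlier in the same sections, the Part A interim rule with 40 patients per dose uses the complementary cut: "If the number of patients who are free from progression at 3 months in either dose is 21 or less", the dose may be dropped. The Protocol gives the risk of continuing when the drug is not "meaningful over no intervention (that is, median TTP = 3 months) is 32"%. The SAP gives the risk of not continuing when "the true median TTP is considered meaningful (that is, median TTP = 4.5 months) is 11"%.

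On scope, since Amendment (c) "the above calculations now only applied to the third interim analysis (for Part B, completed June 2013"). For efficacy endpoints in general, Protocol 12.1 says "no formal hypothesis testing based on a priori power calculations is planned".

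**The concern.** Stopping at 21 or fewer of 40 and passing at 22 or more of 40 are the same cut. The medians are also the same. Yet the Part A paragraph attaches a 32% false-positive risk to that cut, and the Part B paragraph attaches 15%. A first-stage stop can lower the type I error, but halving it is a large effect for one early look at 18 patients, and the text does not make that look binding.

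What is at stake is the weight a reader gives to a Part B pass. At 15% and 78%, a pass would multiply the odds of a good versus a poor treatment by 0.78/0.15 = 5.2. If the real figures are worse, a pass is weaker evidence than the documents suggest. Protocol 12.2.14 says this interim was meant to inform whether second-line patients benefit whatever their AFP level.

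**Working it through.** **Inputs** (all from Protocol 12.2.14, repeated in SAP 5.3.2): p0 = 0.50; p1 = 0.63; n1 = 18; first-stage limit 8; n = 18 + 22 = 40; final cut 22. Under an exponential TTP with median 4.5 months, the 3-month proportion is 0.5^(3/4.5) = 0.630, so p1 agrees with the stated median.

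**1. The documents' own Part A figures.** For a single look at 40 patients:
- P(X ≥ 22 | 40, 0.50) = 0.3179, stated as 32%
- P(X ≤ 21 | 40, 0.63) = 0.1138, stated as 11%

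Both reproduce.

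**2. The Part B rule as worded (no forced stop).** All 40 patients enter, so the decision rests on the final count alone:
- type I error = P(X ≥ 22 | 40, 0.50) = 0.3179
- power = P(X ≥ 22 | 40, 0.63) = 0.8862

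**3. The Part B rule with a binding stop at 8 or fewer of 18.** The probability of a pass is Σ over x = 9 to 18 of P(X1 = x | 18, p) × P(X2 ≥ 22 − x | 22, p):
- p = 0.50: 0.2837
- p = 0.63: 0.8455

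The stop operates with probability 0.407 under the null and 0.085 under the alternative. It lowers the type I error only from 31.8% to 28.4%, because most trials with 8 or fewer of 18 would have failed at 40 anyway.

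**4. Is one number simply misprinted?**

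| Rule, 40 patients | Type I error | Power at 63% |
|---|---|---|
| Stated | 15% | 78% |
| Cut 22, no stop | 31.8% | 88.6% |
| Cut 22, stop at ≤ 8/18 | 28.4% | 84.6% |
| Cut 22, stop at ≤ 9/18 | 23.5% | 77.3% |
| Cut 23, stop at ≤ 8/18 | 20.0% | 78.5% |
| Cut 24, stop at ≤ 8/18 | 12.9% | 69.9% |
| Cut 24, no stop | 13.4% | 71.4% |

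With 22 of 40 held fixed, I searched every first-stage size from 5 to 35 with every first-stage limit. The closest rule (34 patients, limit 19) gives 18.6% and 75.1%.

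The pair is in fact out of reach with 40 patients at 50% versus 63%. The most powerful test at exactly 15% rejects at 24 or more, and at 23 with probability (0.15 − 0.1341)/(0.2148 − 0.1341) = 0.197. Its power is 0.7142 + 0.197 × (0.8125 − 0.7142) = 0.734, below 78%.

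**5. What a pass is worth.** Likelihood ratio of a pass:
- as stated: 0.78/0.15 = 5.20
- no stop: 0.8862/0.3179 = 2.79
- binding stop: 0.8455/0.2837 = 2.98

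A result of exactly 22/40 (55%), with all 40 evaluable at 3 months, has an exact 90% confidence interval of 40.9% to 68.5%, which includes the 50% null.

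**The case against.** The strongest reply is that the documents do not show which number slipped. In Simon's notation a boundary r means rejection above r. Reading 22 that way moves the cut to 23 and gives 78.5% power, which matches the stated 78%. Changing two inputs together also comes near: a cut of 24 with an alternative of 65% gives 12.9% and 78.3%. If the cut-off were the slip, correcting the error rates would attach new figures to a rule nobody intended.

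This does not carry. The shifted cut still gives 20.0% type I error, and the two-change version needs an alternative that the documents do not state. Both documents print 22 or more, both use the complementary limit of 21 in the Part A paragraph, and both say the Part B design keeps the characteristics of the original protocol. The Part A rule was a single look, for a different population, and was never carried out, so it is corroboration rather than a description of Part B. It does corroborate the cut.

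The second reply is that little depends on the figures, and that much stands. The Part B interim was done in June 2013, Part B has completed, and no formal efficacy testing is planned. The planned Part B efficacy analysis is Kaplan-Meier TTP with 90% limits, and the results in Protocol 5.1.5.2 are medians, with no pass or fail against 22 of 40. The odds factors and the interval at 22/40 therefore illustrate the rule, not an observed result. All this limits the consequence, but it does not make 15% and 78% correct.

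**Conclusion.** The stated operating characteristics are wrong for the printed rule. The type I error is 31.8% as worded or 28.4% with a binding stop, which is 2.1 or 1.9 times the stated 15%. The power is 88.6% or 84.6% against 78%. A pass is worth a likelihood ratio of 2.8 or 3.0, not 5.2. The calculation is exact and assumes 40 independent patients, all evaluable at 3 months, with the proportions the documents give. The error makes a Part B pass look stronger than it is. It affects interpretation only: no patient, sample size or planned final analysis turns on it. It is worth correcting because the wrong figures still stand in both documents, close to correct figures for the same cut.

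**What to change.** In Protocol 12.2.14 and SAP 5.3.2, replace 15% and 78% with about 32% and 89% if the first-stage look was non-binding, as the text reads, or with 28% and 85% if it was applied as a binding stop. State which applied. In the Part B report, say that a result of 22 or more of 40 carries that false-positive risk, about twice the one originally stated. Leave the cut-off alone: Part B is enrolled and reported, so a new threshold would be post hoc.

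The cost is one sentence in each of the two documents and one in the report, with the revision of two approved documents that this entails. The stated type I error becomes less favourable. No patients and no new analyses are needed.
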